5.5.1.1 Subgroup Analysis

Supportive subgroup analyses will be conducted following same model as primary efficacy analyses also in addition to by CKD stage strata and by country on the FAS. Subject's dialysis information will be listed by subject, country, and site.

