6.6 Assignment to treatment

6.6.1 Randomisation

Randomisation will be performed using a validated system that automates the random assignment of treatment groups to randomisation numbers. Treatment assignment will be via a central interactive web response (IWR) system in accordance with a pre-planned computer-generated randomisation schedule in a 2:1 ratio.

Randomisation will be stratified according to the following CKD stage strata:

A. ≥40% of subjects must be on dialysis (HD or HDF) and must be CKD stages 4-5

- B. $\geq 20\%$ of subjects must Not be on dialysis and must be CKD stages 4-5
- C. $\geq 20\%$ of subjects must Not be on dialysis and must be CKD stage 3

Randomisation data will be kept strictly confidential, accessible only to authorised persons, until the time of unblinding.

A subject who fulfils the trial eligibility requirements will be randomly assigned to treatment.

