8.2 Sample size and power considerations

Approximately 108 subjects will be randomized in the trial in 2:1 ratio of MC2-25 cream to MC2-25 vehicle, including an assumption of 10% dropouts. For a two-sided test with a 5% level of significance (expected d=1.5 and s=2.46, d/s=0.61) this sample size will provide adequate power (\geq 80%) to compare mean change in WI-NRS from Baseline to Week 12 between MC2-25 cream and MC2-25 vehicle with 72 and 36 subjects (Spencer 2018).

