8.8.1 Primary endpoint

The primary endpoint, mean change in weekly mean WI-NRS recorded in the subject's diary from Baseline to Week 12 for MC2-25 cream compared to MC2-25 vehicle, will be analysed by a mixed model of repeated measures with Baseline weekly mean WI-NRS as covariate and treatment, CKD stage stratum at baseline, systemic CKP-aP treatment status at baseline and visit as fixed factors with a two-sided α =0.05. The weekly mean WI-NRS is calculated as the average of minimum 4 WI-NRS values recorded once daily in the subject's diary from 7 days prior to and including the visit days (i.e., must be recorded for 8 days total).

On the FAS, the primary analysis and one sensitivity analysis will follow a treatment policy strategy irrespective of any potential intercurrent events. On primary analysis, missing values will be replaced following a multiple imputation procedure adequate for the endpoint assuming missingness appearing at random and based on 20 imputations. On the FAS, sensitivity analyses will include imputation by last observation carried forward (LOCF; treatment policy strategy) and multiple imputation of missing data and all data after start of rescue medication (hypothetical strategy).

Applying the same statistical model, further estimands include multiple imputation on the MFAS and as observed on the PPS, both following a treatment policy strategy. If deaths occur, further estimands may be defined following a composite endpoint strategy.

Supportive subgroup analyses will be conducted by dialysis status and CKD stages and by country on the FAS.

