5.2 Handling of Dropouts or Missing Data

5.2.1 Missing Data

For the primary and secondary efficacy endpoints, the primary estimands using the FAS, MFAS and PPS will use a treatment policy strategy for missing data. Missing data will be replaced using a multiple imputation (MI) approach. Note, missing data includes dropouts, empty data fields after dropout date will be handled as missing data regardless of reason for drop out. MI will be performed for all populations separately only if there is a difference in populations. Seed numbers for each endpoint will use the randomly generated 4-digit numbers from the table below. Other variables that are included in the imputation model will include treatment, site, country, visit, and key baseline characteristics such as age, gender, race, CKD stage stratum⁽¹⁾ at baseline, and systemic CKD-aP treatment status⁽²⁾ at baseline. Depending on the pattern of missingness, a 2-step process may be employed. If missing data points occur for an intermediate visit, they will be imputed first using a Markov Chain Monte Carlo (MCMC) method. As a result, a monotone missingness pattern will be obtained for the data to be fully imputed. The subsequent imputation will use general regression for continuous variables and logistic regression for categorical variables under the assumption data are missing at random to produce 20 imputed datasets where the remaining missing data are filled in using 20 separate sets of values. For the categorical secondary variables, the percentages will be calculated from the above imputed data.

- (1) CKD stage stratum at baseline= A. ≥40% of subjects must be on dialysis (HD or HDF) and must be CKD stages 4-5 (CKD stage 4-5 dialysis) B. ≥20% of subjects must Not be on dialysis and must be CKD stages 4-5 (CKD stage 4-5 non-dialysis) C. ≥20% of subjects must Not be on dialysis and must be CKD stage 3 (CKD stage 3)
- (2) Systemic CKD-aP treatment status at baseline will be flagged as "Yes" if prior/concomitant medication falls within one of the ATC groups provided in Section 6.3.2

Table 9 Population and Random Seed Number

Population	Random Seed Number
FAS	6529
MFAS	7631
PPS	9376

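### The subgroup analyses by CKD stratum and country plan no estimate or test of whether the treatment effect differs between subgroups, and they leave the subgroup model unclear

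*SAP*

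**What the plan says.** Protocol 8.8.1 announces the subgroup work in one line: "Supportive subgroup analyses will be conducted by dialysis status and CKD stages and by country on the FAS". SAP 5.5.1.1 gives the method: "Supportive subgroup analyses will be conducted following same model as primary efficacy analyses also in addition to by CKD stage strata and by country". The population there is again the FAS.

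The model referred to is in SAP 5.5.1. It is an MMRM with baseline weekly mean WI-NRS, treatment, CKD stage stratum, systemic treatment status and visit, and an unstructured covariance. Its output is a difference in LS means with SE, 95% CI and p-value. It has no treatment-by-subgroup term. SAP 5.1 makes no multiplicity adjustment.

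The strata come from Protocol 6.6.1 and are repeated in SAP 5.2.1. For stratum A, "≥40% of subjects must be on dialysis (HD or HDF) and must be CKD stages 4-5". Strata B (off dialysis, stages 4-5) and C (off dialysis, stage 3) each have a 20% floor; for C the wording is "of subjects must Not be on dialysis and must be CKD stage 3".

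Neither document gives an interaction or heterogeneity analysis, a minimum subgroup size, or a rule for reading subgroup results.

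**The concern.** The question a subgroup analysis should answer is whether the effect differs between groups. Separate fits do not answer it. They ask in each group whether that group alone reaches p<0.05, and with small groups the answer depends heavily on size and chance. A reader who sees one stratum below 0.05 and two above may take this as evidence that the cream works in one kind of patient and not in others, when the same data are compatible with one common effect.

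There are two gaps of specification as well. The primary model contains CKD stratum as a factor, and that factor is constant inside a stratum, so the same model cannot be applied there without a stated change. And Protocol 8.8.1 names dialysis status, while SAP 5.5.1.1 names only CKD strata and country and otherwise lists dialysis information by subject. SAP 6.2, the table of changes from the protocol, does not mention the difference.

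**Working it through.** **Inputs.** Protocol 8.2 gives the test ("For a two-sided test with a 5% level of significance"), the effect and SD ("expected d=1.5 and s=2.46, d/s=0.61"), the size ("Approximately 108 subjects will be randomized in the trial in 2:1 ratio of MC2-25 cream to MC2-25 vehicle, including an assumption of 10% dropouts") and the arms ("with 72 and 36 subjects"). Minimum stratum shares are 40/20/20%. The number of countries is not stated; four (UK, Germany, Hungary, Poland) is inferred from the EQ-5D-5L value sets in SAP 3.4. Country shares are not given, so equal shares are an assumption.

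**The plan's own figure.** Noncentral-t power for 72 versus 36 is 84.1%. After 10% dropout (64.8 versus 32.4) it is 80.1%. The stated power of at least 80% is reproduced.

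**Power inside a subgroup.** The noncentrality is d / [s × √(1/n₁ + 1/n₂)] on n₁ + n₂ − 2 degrees of freedom. With d = 1.5 and s = 2.46 in every subgroup:

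| Cream/vehicle | Power |
|---|---|
| 43/22 | 63.0% |
| 29/14 | 44.8% |
| 22/11 | 36.0% |
| 21/11 | 35.4% |
| 18/9 (one of four equal countries) | 30.1% |
| 15/7 | 24.5% |
| 14/7 (stratum near its 20% floor) | 24.0% |

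The 95% CI half-width in a 14/7 stratum is 2.09 × 2.46 × √(1/14 + 1/7) = 2.4 points, wider than the 1.5-point effect.

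**Chance of a mixed pattern.** Treating subgroups as independent, P(mixed) = 1 − Πp − Π(1 − p). For strata of 65/22/21, Πp = 0.630 × 0.245 × 0.240 = 0.037 and Π(1 − p) = 0.370 × 0.755 × 0.760 = 0.21, so P(mixed) is about 75%. The same formula over other true effects, equal in all subgroups, with SD 2.46:

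| True effect | Three strata (43/33/32 to 65/22/21) | Four equal countries |
|---|---|---|
| 1.5 | 71-75% | 75% |
| 1.0 | 48-49% | 50% |
| 0.5 | 24% | 27% |
| 0 | 14% | 19% |

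Over all stratum allocations that meet the floors, with 97 to 108 subjects, the range at 1.5 is 69-76%. For countries it is 72-79% over equal and 40/30/20/10 shares. With SD 2.0 or 2.8 and an effect of 1.5, it is 63-87% over strata and countries.

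**What an interaction analysis would give.** For dialysis versus non-dialysis at a 40/60 split, the variance of the difference in effects is s² × Σ[1/(2Nf/3) + 1/(Nf/3)] over f = 0.4 and 0.6.
- The SE is 1.03 with N = 108 and 1.08 with N = 97.
- The 95% CI half-width is therefore about 2.0-2.1 points.
- Power for a 1.5-point difference in effects is 28-31%.
- 80% power needs a difference of about 2.9-3.0 points.
- If the effects are equal, the test flags a difference in 5% of trials per factor.

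**The case against.** The analyses are labelled supportive in an exploratory phase 2 trial, they do not touch the primary test, and the planned output already includes differences with 95% CIs, from which a careful reader would see the overlap. The SAP does not tell anyone to sort subgroups by p<0.05. An interaction test would have low power. All of this stands and limits the weight of the point.

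Four stronger readings are tempting, and the documents do not support them:

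- **A misleading split is the usual result whatever the effect.** It is usual only near the planning effect. At a true effect of 1.0 it occurs in about half of trials, and below that in a minority. Protocol 2.2 itself says that a vehicle effect size cannot yet be established, so 1.5 points over an emollient vehicle is uncertain.
- **The protocol's dialysis analysis has been dropped.** Stratum A is the dialysis group, so its effect would be reported. The protocol wording could also be read as the three-way classification. What is missing is the pooled B+C estimate and the comparison with A.
- **The stratum fits will fail to converge.** Four post-baseline visits need 10 covariance parameters, and a stratum at its floor has about 21 subjects. But the FAS analysis uses multiply imputed, complete data (SAP 5.2.1). Fits to 2,000 simulated complete 14/7 strata, with the stratum term and a separate random subject effect left out, gave no failures. A very small country could still cause trouble; country sizes are not given.
- **This is the main population question for the next trial.** Neither document says so.

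Separate refitting is also an interpretation, though the natural one. Under any reading no interaction is specified.

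**Conclusion.** The point holds as a cheap improvement to a supportive analysis. SAP 5.5.1.1 does not state clearly how subgroup effects are estimated, and neither document plans any estimate or test of whether they differ. On the natural reading, and if the planning effect is the same everywhere, a mixture of p-values on both sides of 0.05 is likely (71-75% across strata) and carries little information about heterogeneity. The likelihood falls with the true effect, as tabulated.

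The figures assume independent subgroup estimates, a common SD of 2.46 and a simple two-sample comparison at Week 12. They do not model precision gained from the baseline covariate and repeated measures; the SD range is the only allowance for it. The country figures rest further on an inferred number of countries and assumed shares.

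**What to change.** Rewrite SAP 5.5.1.1 as one pooled model per subgroup factor on the whole FAS, with a common covariance matrix, the subgroup main effect and the treatment-by-subgroup interaction evaluated at Week 12. Use three factors: dialysis status (stratum A versus B+C), the three CKD strata, and country. In each model say which primary-model terms are replaced or kept, so that stratum is not entered redundantly.

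Report the Week 12 treatment difference with 95% CI for each subgroup, and the interaction estimate with its CI and p-value. Give no within-subgroup p-values, and label the results descriptive. If the reference to dialysis status in Protocol 8.8.1 is meant to be covered by the strata alone, say so in SAP 6.2.

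The cost is a few lines of SAP text and one model per factor; no data collection changes. The drawback is the low power of the interaction test. A non-significant result must not be read as proof of equal effects, so the interval should lead the report.

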5.5.2 Secondary Efficacy Analyses

The key secondary and other secondary endpoints will be analyzed using a generalized estimating equations model with baseline weekly mean WI-NRS as a covariate and treatment,

MC2 Therapeutics Protocol No- MC2-25-C1 V3.0 SAP Final V1.0

CKD stage stratum at baseline, systemic CKP-aP treatment status at baseline and visit as fixed factors and subject as a random factor with a 2-sided $\alpha = 0.05$. An exchangeable covariance structure will be used. Estimates and SE for each treatment group will be displayed along with the difference in estimates between active and vehicle with the corresponding SE, 95% CI and p-value.

Descriptive summaries and listings by subject and visit will be provided.

5.5.3 Other Efficacy Analyses

Descriptive summaries will be provided for all other efficacy endpoints by visit and treatment group. They will also be listed by subject and visit.

The mean change in weekly mean WI-NRS from baseline to Week 1, 4, and 8, respectively, will be analyzed like described for the primary efficacy analysis in Section 5.5.1.

The mean change in weekly mean WI-NRS will be assessed within treatment for both arms (MC2-25 cream and MC2-25 vehicle) for change from baseline for all visits i.e., Week 1, 4, 8 and 12 using a paired T-test.

5.6 Other Safety Variables and Analyses

Safety endpoints will be summarized using the SAS by treatment group and overall and will use descriptive statistics only.

5.6.1 Product Compliance

Subjects enrolled in the trial are required to apply the IMP twice daily during the 12 week double-blind treatment period starting on the day of randomization (Baseline) and ending on the Week 12 visit date (End of Treatment). The total number of IMP applications and the number of missed applications during this period is recorded in the Treatment Application Record on a daily basis and entered in the eCRF.

The applications compliance rate for each subject is defined as:

Compliance = (Actual number of applications in treatment period / Number of expected applications in treatment period) * 100.

Where;

Actual number of applications in treatment period = Total number of applications applied during the course of the trial as reported in the eCRF

Number of expected applications in treatment period = Total number of days from baseline visit (randomization) till Week 12 (EoT) or early withdrawal X 2 (Twice daily application) -2

Duration of treatment period = Total number of days from baseline visit (randomization) till Week 12 (EoT) or early withdrawal

Compliance will be summarized in following categories; less than 80%, \geq 80 to \leq 100% and >100% (in cases where subject used the medication more than prescribed times a day) and average compliance in each treatment arm. Accumulated subject listings will also be presented for compliance.

100% compliance means the subject applied IMP twice daily as prescribed for total number of days in the trial and there were no missed applications between first and last application.

Descriptive statistics will be used to summarize product compliance for the SAS. Subject listing for compliance will be presented by 4-week periods (Baseline to < Week 4, \ge Week 4 to < Week 8, and \ge Week 8 and for overall trial period.

5.6.2 Drug Accountability and Extent of Exposure:

As a part of drug/product accountability, the amount of trial product dispensed and returned (used and unused) will be kept during the trial at each visit and at completion of the trial. Each dispensed kit consists of 5 tubes with each tube having a weight of 74.8 grams (tube with cream and label).

Subjects will return all used and unused tubes at Week 4, 8 and 12 visits and all returned tubes which have broken seals will be weighed to determine the residual amount of the IMP. The following averages will be calculated for all subjects as well as for subjects returning at least 80% of the IMP dispensed during the trial:

- 1. Weight of IMP used during the trial per subject
- 2. Weight of IMP used during the trial per subject per number of weeks on treatment
- 3. Weight of IMP used during the trial per subject per % BSA at Baseline
- 4. Weight of IMP used during the trial per subject per number of weeks on treatment per % BSA at Baseline

Weight of IMP used during the trial per subject = $(74.8 \text{ grams times the total number of tubes returned at Week 4, Week 8, and Week 12 visits) + (50 grams times the total number of dispensed tubes not returned) – (the sum of the weight of all tubes returned at Week 4, Week 8, and Week 12 visits). Notes: The minimum weight of IMP used is 0 grams. Number of weeks on treatment is defined as the period from first to last application expressed in weeks.$

Drug accountability information will be summarized for SAS and listed by subject.

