6.5 Packaging, labelling and storage

MC2-25 cream and MC2-25 vehicle are identical in appearance and packaging.

Medication labels for the IMPs will comply with the legal requirements of the country where the trial is performed and be printed in the local language.

The IMPs will be supplied by MC2's designated vendor and will be stored securely at the site under the control of the investigator. The temperature will be monitored and documented.

The IMP will be supplied to the clinical site(s) as tubes containing 60 g of product. The IMP is to be stored at a temperature of 2° to 8°C at the site, and below 25°C after dispensing to the subject. At all times, the IMP tube should be protected from direct sunlight exposure.

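### The SAP credits 50 g of use for an unreturned tube that the protocol says holds 60 g, and gives no weight for tubes returned sealed

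*SAP*

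**What the plan says.** Protocol 6.5 gives the tube content: "The IMP will be supplied to the clinical site(s) as tubes containing 60 g of product". SAP 5.6.2 gives no net content. It gives a gross weight: "Each dispensed kit consists of 5 tubes with each tube having a weight of 74.8 grams (tube with cream and label").

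The SAP 5.6.2 formula for the amount used by a subject has three terms:

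- plus 74.8 g "times the total number of tubes returned at Week 4, Week 8, and Week 12 visits";
- plus "50 grams times the total number of dispensed tubes not returned";
- minus "the sum of the weight of all tubes returned at Week 4, Week 8, and Week 12 visits".

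The result cannot fall below 0 g.

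Subjects are to bring back both used and unused tubes. On weighing, SAP 5.6.2 says that "all returned tubes which have broken seals will be weighed to determine the residual amount of the IMP", and Protocol 6.8 has the same rule. Neither document says what weight to enter for a tube returned with its seal intact.

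Four averages follow from the formula: total use, use per week, use per % BSA, and use per week per % BSA. Each is reported for all subjects and again for "subjects returning at least 80% of the IMP dispensed during the trial".

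**The concern.** The formula treats an unreturned tube as used up, but its 50 g credit is not the content that the protocol states. SAP 6.2 lists two changes from the protocol, one to the complete-response threshold and one to the biopsy biomarkers, and neither concerns tube content. A reader cannot tell whether 50 g is a slip, a correction of the protocol, or a deliberate assumption about lost tubes.

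The sealed-tube gap is separate. The formula subtracts a quantity that the weighing rule does not collect for every tube, so the programmer has to choose a value that the SAP does not give.

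At stake are the weight-based exposure summaries of a first-in-human topical product. Protocol 8.5 names total and average weight used among the exposure measures, and the safety-margin argument in Protocol 2.3 is expressed in grams of cream per day. Weighing is also a check on exposure that does not rest on the subject's own record of applications.

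**Working it through.** **Inputs**

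- Net fill: 60 g (Protocol 6.5).
- Gross weight of a full tube: 74.8 g; 5 tubes per kit (SAP 5.6.2).
- Credit per unreturned tube: 50 g (SAP 5.6.2).
- Tare (empty tube with label): not stated. It is 74.8 − 60 = 14.8 g if the fill is 60 g, and 74.8 − 50 = 24.8 g if the fill is 50 g.

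**Formula**

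Used = 74.8 × (tubes returned) + 50 × (tubes not returned) − (summed weight of tubes returned), with a floor of 0.

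**Step 1: can the 50 g be reproduced?** An emptied tube that is returned counts as 74.8 g less the tare.

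| Assumed fill | Tare | Emptied, returned | Emptied, not returned | Difference |
|---|---|---|---|---|
| 60 g | 14.8 g | 60 g | 50 g | −10 g (10/60 = 16.7%) |
| 50 g | 24.8 g | 50 g | 50 g | 0 g |

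The 50 g follows only from a 50 g fill, which contradicts Protocol 6.5.

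**Step 2: size per kit.** Take a 60 g fill, one 5-tube kit, all tubes emptied and none returned sealed. The true use is 5 × 60 = 300 g.

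| Tubes not returned | SAP formula | With a 60 g credit |
|---|---|---|
| 1 | 290 g | 300 g |
| 2 | 280 g | 300 g |
| 5 | 250 g | 300 g |

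If the 80% return subset is counted in tubes, at most 1 tube in 5 is missing, so the shortfall is at most 10 g per 300 g dispensed (3.3%).

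**Step 3: sealed returned tubes.** Each adds 74.8 g through the first term. What the last term removes depends on the weight entered:

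- entered at 74.8 g, or actually weighed: 74.8 − 74.8 = 0 g used;
- missing weight summed as zero: 74.8 − 0 = 74.8 g used, more than the tube holds;
- missing weight carried through: the subject's total becomes missing.

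**Step 4: both together.** An illustrative kit has 3 tubes emptied and returned, 1 returned sealed and 1 not returned, with a tare of 14.8 g.

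- 50 g credit, sealed tube at 74.8 g: 74.8 × 4 + 50 − (3 × 14.8 + 74.8) = 299.2 + 50 − 119.2 = 230.0 g.
- 60 g credit, sealed tube at 74.8 g: 299.2 + 60 − 119.2 = 240.0 g.
- 50 g credit, sealed tube summed as zero: 299.2 + 50 − 44.4 = 304.8 g.

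The two effects run in opposite directions. Nothing makes them cancel.

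**The case against.** The SAP does not say that a tube holds 50 g. The figure is a credit for a tube whose true use is unknown, and it could be a deliberate allowance for tubes lost before they were empty. That possibility stands, and it is why the direction of the error is conditional. It does not remove the point, because no such reasoning is stated and the departure is not listed in SAP 6.2. Opened tubes that come back are handled by the difference in gross weight, so neither fill nor tare affects them.

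A reader might infer that the formula counts every sealed returned tube as 74.8 g used. The text does not support that. The first and last terms both cover all returned tubes, so a sealed tube nets to about 0 g as written. The floor at 0 g fits that reading, since it is needed only when returned weights can reach or exceed the nominal total. The 74.8 g error needs a programmer to treat an uncollected weight as zero, which nothing in either document instructs. What stands is the missing default weight.

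A reader might also take the 80% subset to mean subjects who used 20% or less of their cream. Read by weight of product, the phrase does say that. But SAP 5.6.2 speaks throughout of tubes returned, used and unused, so a count of tubes is the evident meaning. This is a matter of wording only.

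**Conclusion.** The 50 g credit is wrong as written, in that it cannot stand beside the protocol's 60 g without an explanation. If the fill is 60 g and an unreturned tube is taken as emptied, use is understated by 10 g (16.7%) per such tube. If the fill is 50 g, the SAP formula is consistent with itself and Protocol 6.5 needs correcting. The documents do not settle which holds.

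The sealed-tube point is an omission. It leads to an error only if sealed tubes are returned and their missing weights are handled badly. It would be too strong to say that the exposure figures will be wrong: both effects depend on how many tubes are not returned or come back sealed, which the documents cannot tell us.

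The reach is limited to the four descriptive averages in SAP 5.6.2. One might suppose that these weights feed an analysis relating effect or safety to the amount applied, but neither document plans one. The efficacy models (SAP 5.5), the adverse-event summaries (SAP 5.6.4) and the application-count compliance rate (SAP 5.6.1) do not use the formula.

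**What to change.** Before database lock:

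1. Confirm the net fill with the supplier. If it is 60 g, credit 60 g per unreturned tube, or keep 50 g with a stated reason and an entry in SAP 6.2. If it is 50 g, correct Protocol 6.5.
2. State that a tube returned with its seal intact counts as 0 g used, either by entering it at 74.8 g or by leaving it out of both the first and the last term.
3. As a clarification of wording, define the second reporting set as subjects who returned at least 80% of the tubes dispensed to them.

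The cost is a few sentences in SAP 5.6.2 and 6.2 and a few lines of code. No new data are needed beyond whether each returned tube was sealed, which sites must already establish to decide which tubes to weigh. If Protocol 6.5 is the text in error, its correction follows the amendment rules in Protocol 9.1.
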